9.3.1.3 Stopping Rule Monitoring

The Investigator is responsible for completing efficacy/safety summary reports and submitting them to the IND Office Medical Affairs and Safety Group, for review. These should be submitted after the first 15 evaluable subjects, complete 6 cycles of study treatment, and again after the total of 25 evaluable subjects, complete 6 cycles of therapy.

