9.1 Statistical Analysis Plan

This is a Phase II, open label, single arm study, evaluating the efficacy and safety of sintilimab in subjects with UPS. Up to 25 subjects with UPS will be enrolled.

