9.3.1.2 Design and sample size/power

The primary efficacy endpoint will be confirmed ORR at 12W. A patient will be considered as a responder to the treatment if he/she has achieved confirmed complete response (CR) or partial response (PR) determined by RECIST 1.1.

A Simon's two-stage Minimax design will be used to monitor the efficacy of sintilimab. The null hypothesis involves an ORR of 10% that will be tested against an ORR of 30%, i.e. a 20% improvement. In the first stage, 15 patients will be treated. If there is ≤ 1 patient who achieves objective response in these 15 patients, the study will be terminated. If the study moves forward to second stage, an additional 10 patients will be treated leading to a total of 25 patients. Six or more responders out of the 25 treated patients will be considered clinically relevant to justify further investigation. The power of this design is 80% under the 1-sided type I error rate of 5%. The early stopping probability is 55% if the ORR is 10% and the average sample size would be 19.5. Assuming a 5% dropout rate, we will need to enroll up to a total of 27 patients.

Analysis of key and other secondary efficacy endpoints

The key secondary efficacy endpoints are ORR (RECIST 1.1), DCR, DOR, PFS and OS in the evaluable and ITT populations.

The ORR, DCR and corresponding exact 95% CIs of the sintilimab arm will be estimated using binomial distribution.

PFS is the time from first dose to first date of Investigator-determined progression (by imaging),

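### The stopping-rule reports wait for evaluable subjects to finish six cycles, with no provision for early stops, and the rule's denominator and the enrolment total differ between sections

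*Combined protocol and SAP*

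**What the plan says.** **Timing.** Section 9.3.1.3 has the investigator send efficacy and safety summaries to the IND Office twice. The first submission is timed thus: "These should be submitted after the first 15 evaluable subjects, complete 6 cycles of study treatment". The final one has the same form, with all 25 evaluable subjects in place of the first 15. No other section dates either look. Section 3.3 mentions an interim analysis and Section 10.1 an external monitoring board, both without a time.

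**Decision rule.** Section 9.3.1.2 works in treated patients. At stage 1, "In the first stage, 15 patients will be treated", and the trial ends if at most one responds. Then: "If the study moves forward to second stage, an additional 10 patients will be treated leading to a total of 25 patients". Success is defined the same way: "Six or more responders out of the 25 treated patients will be considered clinically relevant to justify further investigation". The section adds: "The early stopping probability is 55% if the ORR is 10% and the average sample size would be 19.5".

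**Denominator elsewhere.** Section 3.1 plans 25 evaluable subjects. Section 9.2 defines the evaluable set as measurable disease at baseline plus at least one restaging, sets no minimum number of cycles, and assigns that set to ORR. Section 9.3.1.1 defines the primary endpoint in it.

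**Enrolment.** Section 9.3.1.2: "Assuming a 5% dropout rate, we will need to enroll up to a total of 27 patients". Section 9.1: "Up to 25 subjects with UPS will be enrolled".

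**Early stops.** Section 4.4.1 lists mandatory reasons to stop treatment, including progression at week 12 or later. Section 4.4.2 bars replacement of anyone who has received a study intervention.

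**The concern.** In this disease some patients will leave treatment before six cycles. The trigger does not say what happens to the report when one of them is among the 15 or the 25. Followed as written, the stage-1 report may have no valid date, and the final report needs almost every enrolled patient to finish six cycles. A futility rule should not depend on readers inferring its timing.

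The denominator is a separate matter and does not depend on how the timing is read. A patient who dies before the first restaging scan is one of the 15 or 25 treated in Section 9.3.1.2, but is not in the evaluable set that Sections 9.2 and 9.3.1.1 use for the same endpoint. The same data could therefore give two different answers at a boundary of 1/15 or 6/25.

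**Working it through.** **1. The plan's own figures reproduce.** Stop if ≤1 of 15 respond; success if ≥6 of 25.
- Early stopping at a 10% ORR: 0.9^15 + 15 × 0.1 × 0.9^14 = 0.206 + 0.343 = 0.549 (stated 55%).
- Average N: 15 + 10 × (1 − 0.549) = 19.51 (stated 19.5).
- Exact one-sided type I error: 0.0328 (0.0334 if the stage-1 stop is ignored). Power at 30%: 0.802.
- Dropout: 25 / 0.95 = 26.3, rounded up to 27.

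**2. When six cycles end.** Table 1 puts the Cycle 6 dose at Day 106 (week 15), so the cycle ends at week 18. Scans are six-weekly at first: weeks 6, 12 and 18. A patient found to have progressed at week 6 or 12 can therefore stop before Cycle 6.

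**3. Tolerance of the literal trigger.** First report: 15 − 15 = 0 early stops among the first 15 evaluable subjects. Final report: 27 − 25 = 2 with 27 enrolled, 25 − 25 = 0 with 25. Patients without a restaging scan use up the same allowance.

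**4. Share completing six cycles (q).** The documents do not give it, so it is an assumption. Section 1.1.2 cites median PFS of 3 months (40 UPS patients) and 7 months (first 10 patients) on another PD-1 antibody. With exponential PFS, the share progression-free at week t is 0.5^(t/m), where m = 13.04 weeks (3 months) or 30.44 weeks (7 months).
- Low: m = 13.04 at week 12 gives 0.53 (everyone found progressing by week 12 stops).
- Middle: m = 13.04 at week 6 gives 0.73 (stable week-12 progressors continue to the next scan, as Section 7.1.2 allows).
- High: m = 30.44 at week 6 gives 0.87.
- Inside this range: 0.659, the pooled-tumour share reaching at least five cycles in Section 1.2.2; the six-cycle share there cannot be higher.
- Outside it: 0.38 (m = 13.04 read at week 18) and 0.95 (the 5% dropout is the only cause of early stopping).

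**5. Chance that the literal triggers are met**, with completion independent between patients and every enrolled patient taken as evaluable:

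| q | First 15 all complete, q^15 | ≥25 of 27 complete | 25 of 25 complete, q^25 |
|---|---|---|---|
| 0.38 | <0.0001 | <0.0001 | <0.0001 |
| 0.53 | 0.00007 | 0.00001 | <0.0001 |
| 0.659 | 0.0019 | 0.0014 | <0.0001 |
| 0.73 | 0.0089 | 0.012 | 0.0004 |
| 0.87 | 0.124 | 0.300 | 0.031 |
| 0.95 | 0.463 | 0.850 | 0.277 |

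If the first report instead waits for any 15 completers, it needs on average 15/q subjects: 28.3, 20.5 and 17.2 at q = 0.53, 0.73 and 0.87.

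**6. Conditional illustration only.** Suppose the look waits for the 15th completer **and** accrual is not held. Let N15 be the number treated by then (negative binomial, capped at 25), with completion independent of response and no time lag. At a 10% ORR, the chance of stopping before 25 are treated is 0.549 × P(N15 < 25), and average N is 0.549 × E[min(N15, 25)] + 0.451 × 25. For q = 0.53 / 0.73 / 0.87:
- P(N15 < 25) = 0.234 / 0.914 / 0.9995, so stopping probability is 0.13 / 0.50 / 0.55.
- E[min(N15, 25)] = 24.35 / 20.44 / 17.24, so average N is 24.6 / 22.5 / 20.7.

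**The case against.** The best defence has four parts.

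*Section 9.3.1.3 is a reporting clause; the decision rule is complete in Section 9.3.1.2.* This stands in part. The rule itself is sound, and the 12-week endpoint limits how early stage 1 can be judged. But no other section dates the looks, so the reporting clause sets their timing in practice.

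*Six cycles is shorthand for week 18, when a response first seen at week 12 would have its next scheduled scan.* This is plausible, and a look at about that time is not wrong in itself. The text nonetheless asks for completion by evaluable subjects, and nothing in the evaluable-set definition supplies the missing provision for early stops.

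*Harm to the operating characteristics needs accrual past 15 before the look.* This stands. A reader might infer that the 55% and 19.5 are lost, or that the ten stage-2 patients will be exposed to an inactive drug. The documents do not support that: Section 9.3.1.2 makes stage 2 conditional on stage 1. Under that sequence the figures hold, and a late report lengthens the pause. Step 6 of the working is therefore an illustration, and even there stopping probability is unchanged at q = 0.87.

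*The denominators nearly coincide, because Section 3.1 speaks of evaluable subjects who are enrolled and treated, and 27 allows for dropout.* The gap may be only about two patients, but the boundaries are single counts, and Section 9.1 does not include the allowance.

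**Conclusion.** The point holds as a defect of wording and consistency in the stopping rule. It is not an error in the Simon design. Three parts rest on the text alone: the trigger has no provision for early stops; the decision rule counts treated patients while four other sections count evaluable ones; and the enrolment totals are 25 and 27. The literal tolerance (none at the first look, two or none at the final one) is plain arithmetic.

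How likely the literal triggers are to fail rests on the assumed completion share. Over 0.53 to 0.87 the first is met with probability below 0.001 to 0.12 and the final one, with 27 enrolled, with about 0 to 0.30. If dropout were the only cause of early stopping (0.95), these rise to 0.46 and 0.85. PFS on another drug is only a proxy for time on treatment, and the 7-month median comes from ten patients.

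Two stronger conclusions should not be drawn. Type I error is not inflated: it is 0.033 with or without the stage-1 stop. The stated stopping probability and average sample size are not shown to be lost: that would need both the assumed completion share and accrual continuing before the look.

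**What to change.** - **Section 9.3.1.3:** make each report due when each of the first 15 (then all 25) treated subjects either has had the scans that determine confirmed response or has earlier progressed, died or discontinued.
- **Denominator:** apply the 1/15 and 6/25 rule to treated patients, as Section 9.3.1.2 already does, and count those without a confirmed response as non-responders. Report the evaluable-set ORR as supportive. Align Sections 3.1, 9.2, 9.3.1.1 and 9.3.1.3.
- **Enrolment:** give one total in Sections 9.1 and 9.3.1.2. If 27 is kept, say that the rule is read on the first 25 treated.
- **Accrual:** state in Section 9.3.1.3 that stage-2 enrolment waits for the stage-1 result or for the second confirmed response, whichever comes first.

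The cost is a few sentences; boundaries, sample size and power are unchanged. The downsides are a possible short accrual pause, which the two-stage design already implies, and a slightly lower ORR estimate, because treated patients with no restaging stay in the denominator.

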9.3.2 Safety analysis

The safety analysis will use the SS. Safety parameters include AEs, laboratory tests, vital signs, ECG, immunogenicity, etc.

9.3.2.1 Drug exposure

The amount of drug exposure and duration of treatment (number of treatment cycles) will be summarized.

9.3.2.2 AEs

The incidence (frequency) of AEs, TEAEs, TRAEs, irAEs, SAEs, resulting in treatment

discontinuation, and AEs resulting in death will be summarized. The severity distribution of TEAEs, TRAEs, and irAEs will be summarized using NCI CTCAE v5.0 presented via SOC/PT.

Subjects who discontinue the treatment due to AEs, develop SAE, or die will be listed (include at least the followings: start and end dates of the AEs, severity grades, relationship with study drugs, measures taken, and outcomes).

9.3.2.3 Laboratory tests

Abnormalities in hematology and biochemistry will be assessed through laboratory parameters. Each laboratory test result will be graded according to NCI CTCAE v5.0. The number of subjects with laboratory abnormalities at baseline will be presented by severity grade. Laboratory parameters measured on the day of first dose of study treatment (Day 1 of Cycle 1) will be considered as baseline measurements. The treatment phase for all laboratory parameters begins on Day 1 of study treatment.

The frequency of laboratory abnormalities of each subject during the treatment phase will be summarized by severity grade. The worst grade (most severe) for each subject will be used if the same laboratory parameter was found to be abnormal repeatedly. All the laboratory parameters will be summarized by the worst NCI grade.

Cross-classification tables describing changes in frequency of any given laboratory parameter before and after treatment based on NCI grades will be provided.

Lists of subjects with laboratory abnormalities \geq grade 3 will be provided.

For any given laboratory parameter, a subject is considered evaluable if at least one measurement is available.

Routine urinalysis: A cross-classification table is used to describe changes between normalities and abnormalities before and after the treatment.

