6. Complete blood count: red blood cell (RBC) count, HGB, white blood cell (WBC) count, PLT count, WBC differentials [lymphocyte (LYM) count and ANC]. Blood biochemistry: hepatic function [TBIL, ALT, AST, alkaline phosphatase (ALP), albumin (ALB), total protein (TP), and lactate dehydrogenase (LDH)], renal function [urea (UREA) and Cr], electrolytes (Na, K, Cl, Mg, Ca, and P), amylase, and blood glucose (BG). Routine urinalysis: pH (PH), urine white blood cell (UWBC), urine protein (UPRO), urine red blood cell (URBC), and urine glucose (UGLU), will be performed within 7 days prior to the first dose during screening, and during the end-of-treatment visit. Complete blood count and blood biochemistry are performed within 7 days prior to the first dose during screening, within 3 days prior to each dose, during the end-of-treatment visit, and during the first safety follow-up. Tests will be conducted in each local lab.
7. Coagulation function tests: PT and INR. The test will be conducted within 7 days prior to the first dose. Tests will be conducted in each local lab.
8. Women of childbearing potential will undergo a blood pregnancy test within 3 days prior to the first dose and during the end-of-treatment visit and a urine pregnancy test will be done prior to every other cycle from Cycle 2 onwards. If the urine pregnancy test is not conclusive, then a blood pregnancy test should be performed. The conclusion should be based on the blood pregnancy test. Tests will be conducted in each local lab.
9. The tests will be conducted during screening, within 3 days prior to the administration of the study drug from Cycle 2 onwards, prior to every other cycle and during end-of-treatment visit. Thyroid function tests: thyroid stimulating hormone (TSH), free triiodothyronine (FT3), and free tetraiodothyronine (FT4). Tests will be conducted in each local lab.

10. Hepatitis B panel (HBsAg, HBsAB, HBCAB), HCV antibody, and HIV antibody will be tested during screening. If the result shows HBsAg positive, then HBV DNA test should be further conducted. If the result shows HCV antibody positive, then HCV RNA test should be further conducted. The results obtained within 28 days prior to start of therapy can be accepted. Prophylactic antiviral therapy is suggested to be performed according to the local treatment guidelines for HBV carriers. Tests will be conducted in each local lab.

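### Section 9.3.2.3 puts a pre-dose Day 1 laboratory value in both baseline and treatment phase, and counts subjects with no post-dose value as evaluable

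*Combined protocol and SAP*

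**What the plan says.** All the analysis rules are in Section 9.3.2.3 (Laboratory tests) of the combined protocol and SAP:

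- Baseline: "Laboratory parameters measured on the day of first dose of study treatment (Day 1 of Cycle 1) will be considered as baseline measurements".
- Treatment phase: "The treatment phase for all laboratory parameters begins on Day 1 of study treatment". Nothing limits this to samples taken after the infusion, and nothing removes the baseline sample.
- Summary: "The frequency of laboratory abnormalities of each subject during the treatment phase will be summarized by severity grade". For repeated abnormalities, "The worst grade (most severe) for each subject will be used if the same laboratory parameter was found to be abnormal repeatedly", and "All the laboratory parameters will be summarized by the worst NCI grade". No increase over the baseline grade is required.
- Evaluability: for any parameter, "a subject is considered evaluable if at least one measurement is available".
- Cross-classification tables by NCI grade are promised for the periods before and after treatment. Which value represents the later period (worst, last or end of treatment) is not stated.
- Baseline abnormalities are tabulated separately by grade.

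Sample timing comes from Table 1 and its notes. Blood counts and chemistry are marked at Cycle 1 Day 1, and note 6 has them drawn "within 3 days prior to each dose". Section 6.2.2, by contrast, is headed as a baseline before Day 1 of Cycle 1.

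**The concern.** A scheduled Day 1 sample is taken before any sintilimab has been given, yet by calendar day it belongs to the treatment phase as well as to baseline. A worst-grade summary over that phase then carries the pre-treatment grade forward. The evaluability rule does not require any post-dose value, so a subject with only a pre-dose sample can sit in the denominator of a treatment-phase rate.

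Safety is a secondary objective and the study has one arm, so no control rate would expose either distortion. Abnormal values at entry are admissible. Section 4.1 allows bilirubin to 1.5 x ULN, ALT and AST to 2.5 or 5 x ULN, hemoglobin down to 8.0 g/dL and platelets down to 75 x 10^9/L. Exclusion criterion 8 exempts asymptomatic laboratory abnormalities left by prior therapy.

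**Working it through.** The plan states no figure on this point, so there is none to reproduce. The check sets the definitions side by side and then works through their consequences.

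**1. Where each sample falls, read literally**

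| Blood count or chemistry sample | Baseline? | Treatment phase? |
|---|---|---|
| Day 1, before the infusion | yes | yes |
| 1 to 3 days before Day 1 (allowed by note 6) | no | no |
| Later cycles | no | yes |

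**2. Effect on the worst grade.** Let a be the Day 1 grade and c the worst post-dose grade, each 0 to 4, giving 5 x 5 = 25 possible pairs. With Day 1 inside the window the recorded grade is max(a, c), which cannot be below a.

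- Pairs where the post-dose grade is better (c < a): 4 + 3 + 2 + 1 = 10.
- Pairs where the recorded grade is better (max(a, c) < a): 0.
- Pairs abnormal on Day 1 and normal at every later test (a > 0, c = 0): 4. Only these create an on-treatment abnormality that did not occur.
- In the other 10 - 4 = 6 pairs the subject is still abnormal after dosing. The recorded grade is too high, but the any-grade count is right.

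These are counts of possible patterns, not probabilities.

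**3. Size of the overlap.** Let p be the share of subjects abnormal on a Day 1 draw and s the share of those who are normal at every later test. The number wrongly added to the any-grade count is N x p x s. The documents give neither p nor s. The illustration below assumes N = 25 (Section 9.1), with every subject sampled on Day 1:

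- p = 20%, s = 25%: 25 x 0.20 x 0.25 = 1.25 subjects (5 points).
- p = 40%, s = 50%: 25 x 0.40 x 0.50 = 5.0 subjects (20 points).
- s = 0: no subjects, whatever p is.

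Over p = 10 to 40% and s = 0 to 50%, the addition runs from 0 to 5.0 subjects. Subjects sampled before Day 1 add nothing.

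**4. Removing the overlap is not enough.** Take p = 20%, s = 25% and assume 15% new abnormalities among subjects normal at baseline. The post-dose count is 25 x (0.20 x 0.75 + 0.80 x 0.15) = 3.75 + 3.00 = 6.75, against 25 x (0.20 + 0.80 x 0.15) = 8.00 with the overlap. Of the 6.75, the 3.75 were already abnormal before treatment. They stay in the table unless a grade increase is required.

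**5. Denominator.** Assume 5 subjects with a post-dose abnormality, and 1, 2 or 3 of 25 subjects with only a normal baseline value. The one-measurement rule gives 5/25 = 20.0%. Requiring a post-dose value gives 5/24 = 20.8%, 5/23 = 21.7% or 5/22 = 22.7%. This error lowers the rate.

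**The case against.** The best defence is that Section 9.3.2.3 expressly assigns the Day 1 value to baseline, and that a table comparing before with after presupposes two separate periods. A sensible programmer would leave the baseline sample out of the treatment phase. Baseline grades are also tabulated on their own, Section 9.3.2.2 summarises TEAEs, and Sections 8.1 and 8.3.3 count a pre-existing condition as an AE only if it worsens. No test or stopping threshold uses the laboratory tables. All of this limits the harm, but none of it corrects the treatment-phase counts if the rules are followed as written.

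A reader might draw four stronger conclusions that the documents do not support:

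- **That shift tables can never show improvement.** This holds only if the undefined later value is the worst grade over a window that includes Day 1, and then only for subjects sampled on Day 1. The worst-grade sentence makes that reading plausible, but the plan does not state it.
- **That everyone who improves is a false on-treatment abnormality.** A subject who improves but stays abnormal belongs in the any-grade count.
- **That pre-dose abnormalities will be common.** Entry limits show what is admissible, not how often it occurs.
- **That coagulation will be reported with a false zero rate.** Note 7 schedules coagulation only before treatment ("The test will be conducted within 7 days prior to the first dose"). But Section 9.3.2.3 opens with hematology and biochemistry, and nowhere is a treatment-phase coagulation rate promised.

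**Conclusion.** The point stands as a defect in stated rules, confined to descriptive safety tables. For blood counts and chemistry drawn on Day 1, the baseline and treatment-phase definitions overlap, and a pre-dose abnormality that resolves is counted as on-treatment. Samples drawn one to three days earlier are assigned to neither period. The evaluability rule is a separate fault and works in the opposite direction, diluting rates.

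The overlap effect is p x s, which the documents do not allow to be estimated; the 0 to 5.0 subjects in 25 is an illustration under assumed shares with every draw on Day 1. The 20.0% against 20.8% to 22.7% is likewise assumed. Loss of improvement in the shift tables is conditional on how the later value is chosen. The primary ORR analysis is not affected.

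**What to change.** Replace the baseline, treatment-phase and evaluability sentences of Section 9.3.2.3 with:

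> Baseline is the last non-missing value before the first infusion. The treatment phase begins after the start of the first infusion; pre-dose values are excluded. Treatment-emergent abnormalities are those with a grade increase from baseline. Shift tables compare baseline with the worst post-dose grade. A subject is evaluable for treatment-phase summaries only with at least one post-first-dose value, and for shift tables only with a baseline and at least one post-first-dose value.

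The baseline sentence also settles samples drawn before Day 1. The grade-increase sentence is needed because persisting abnormalities would otherwise still be tabulated as on-treatment. The cost is a few sentences, and denominators of some descriptive tables may fall by a few subjects. No extra sampling is needed.
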